Educational attainment	X		
Health literacy –S-TOFHLA, ANQ, eHealth Literacy	X		
Comorbidities	X		
Depressive thoughts	X		
Primary language	X		

*Quarterly data collection occurs at months 3, 6, 9, and 12 and every 3 months after month 12 until the end of the study.

** We collect outcomes quarterly, at 12 months, and every 3 months until the study ends. Final visit is the final visit of data collection that occurs after the 12-month collection.

+Prednisone bursts are defined as a new prescription or an increase in dose of prednisone.

++FEV1 could be collected for only 203 patients owing to non-availability of spirometry equipment at the start of the study.

#The Inhaler Adherence Scale asks participant's report of non-adherence.^{29,30} It is a 6-item scale with each item scored 1 (non-adherence) or 0 (adherence). The range is 0-6, with 0 being optimal adherence.

Time frame for the study

All participants were to be followed for data collection every 3 months for at least 1 year (please see the Home Visitor Protocol sub-section and Figure 1). We chose a 3-month interval for data collection, as the Expert Panel Report uses 3 months for making a change such as “stepping down.”³¹ We chose the times for home visits, based on [name] experience with home visits in children. She found it was important to have home visits early in participation.³² We wanted the last 6 months to be for observation to assess sustainability. For reasons for withdrawals or becoming lost to follow-up, please see Figure 2.

Data collection and sources

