The sensitivity analyses we have described (#1) make assumptions that the dropout and visit times are not related to the values of outcomes, i.e., that dropout is at random and that visit times are ignorable. Our dropout was limited, but irregular interview times were common. Global sensitivity analyses are now available but only when visit times are regular.⁵⁰ Methods for irregular visits are awaiting methodological development ([name], personal communications 04/2017). Details appear in Appendix A7.

Sensitivity Analysis #3. Non-adherence to home visit protocol

As randomized analyses do not answer the question of the effect of an intervention if the patients adhere to the protocol, simplistic approaches to per-protocol analysis can be biased. Although weighting methods can generate unbiased estimate of the effect of a treatment under full adherence,⁵¹⁻⁵³ we could not adopt these methods because they assume regular observation times. Use of weighting approach for irregular outcome times awaits methodological development. For that reason, we implemented an alternative based on instrumental variables.

Instrumental variable methods adjusted for differences in the characteristics of patients who received all home visits and those who did not.⁵⁴ In our case the instrument was

randomization at baseline. These methods require several assumptions.⁵⁵ Details along with the specific method we used (two- stage residual inclusion) appear in Appendix A10.

Missing Data

Missing baseline data

Missing covariate data were infrequent, but some patients were missing an element of a questionnaire, or responded “did not know”. We created latent classes of covariates for both confounder control and for estimating effect modification (please see below).

Missing data for effect modifiers

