Appendix A4. Appointments kept among asthma patients.

Background

The goals of this analysis were: first, to use treatment assignment as the exposure of interest, in an as-randomized analysis, to estimate the association of treatment assignment and appointments kept over time; and second, in an exploratory observational analysis, to examine the possible association of the time-varying factor of having regular appointments (with treating physicians) and asthma control. The underlying hypothesis was that the home-visitors might be a positive influence in reminding patients to keep regular appointments, and that regular appointments might in turn lead to improved asthma control among patients.

Data Management Methods

We obtained data on appointments from the two participating health systems (Penn Medicine and Temple Health) on the enrolled patients for the time during their study participation. With these data, we then identified all appointments that were made and kept by the patients and the dates of those appointments. Then we determined whether a patient had kept an appointment within 6 months of the date of interview. This variable was binary (0/1) and repeated for each patient over time. We allowed a kept appointment to satisfy the condition of "appointment within 6 months" for more than one interview date.

Statistical Methods

The proportion of patients with 0 to 5 data collection interviews with a kept appointment within 6 months was compared across intervention groups using a Chi-square test of association.

Using a longitudinal model similar to that used for the main analysis of the association of treatment assignment (home visitor versus portal only) we adjusted for baseline covariates (including treatment assignment). An appointment kept within six months (yes/no) was the time-varying exposure of interest. Time in the model was again fit with marginal splines. Together with a main effect for kept appointment, we added time-by-kept appointment interaction terms. We used a marginal model (generalized estimating equations) with a log link and a gamma family, to be consistent with the other models for asthma control.

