Typically reports of longitudinal studies use time as a categorical factor. When all patients are measured at the same time, this analytic approach is entirely appropriate. For such studies as ours, however, this approach was both not feasible and theoretically unsound. For that reason we modeled actual data collection times using a flexible approach – marginal splines.

As with many studies, and in particular as with studies that involve mostly disadvantaged patients who also have underlying comorbidities that limit their mobility, contact and meeting availability with research personnel for the preplanned data collection times, this difficulty presents challenges. The preplanned times were 0, 12, 24, 36, and 48 weeks from randomization. But patients could not be contacted and interviewed at these times due to the previously mentioned challenges. This reality led to measurements at times that differed from, but mostly followed, the preplanned times. With irregular data collection times, we therefore used the following method of analysis.

Methods for irregular data collection times

- (1) For analysis, we used all data whenever obtained. No interviews were considered to be out of range. We used all interviews even for those patients who dropped out after baseline interviews but before the completion of the fifth and final interview.
- (2) Unlike many studies, we modeled time as a continuous measure rather than as a categorical factor. We recorded and used for each patient the actual time (months from randomization) of the interview.
- (3) With continuous time, we needed then to allow for non-linear trajectories of outcomes over time. We made no assumptions about linear trends in health improvement arising out of the

Appendix A7 (continued). Methods for handling Irregular data collection interviews - Unified modeling approach.

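### The only randomised comparison of appointments kept is a chi-square on a 0-to-5 interview count with no denominator, so unequal interview completion could create or hide an effect

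*Combined protocol and SAP*

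**What the plan says.** The first goal of Appendix A4 (Background) is "to use treatment assignment as the exposure of interest, in an as-randomized analysis". What that analysis is meant to do is "to estimate the association of treatment assignment and appointments kept over time". The data are one yes/no value for each interview held: "This variable was binary (0/1) and repeated for each patient over time". Under Statistical Methods, only one quantity serves this goal: "The proportion of patients with 0 to 5 data collection interviews with a kept appointment within 6 months". The plan then states how the arms are set against each other on it, namely that it "was compared across intervention groups using a Chi-square test of association". The longitudinal model that follows in the same appendix has asthma control as its outcome and kept appointment as its exposure, so it is not a second randomised comparison of appointment keeping.

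Other sections bear on this:

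- Appendix A7 (Methods for irregular data collection times) plans five interviews, at 0, 12, 24, 36 and 48 weeks. It keeps "patients who dropped out after baseline interviews but before the completion of the fifth and final interview".
- A footnote to Table 2 has interviews continuing "every 3 months after month 12 until the end of the study". How these enter a count capped at 5 is not stated.
- On the amount of dropout, Sensitivity Analysis #2 says: "Our dropout was limited, but irregular interview times were common". The available text gives no figure by arm. Figure 2, which the plan cites for withdrawals, is not reproduced in that text.
- The Mediation section treats portal use as a rate because follow-up time varied. It also makes the arm-to-mediator association a precondition for any mediation.
- Appendix A5 gives the third mediator, inhaler adherence, a longitudinal model.

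**The concern.** A missed interview cannot add to the count. A patient with two interviews scores at most 2, however regularly they attend. The count therefore mixes how often patients kept appointments with how often they were interviewed, and an arm difference in the second can pass for a difference in the first or cancel it. The plan corrects for this with portal use but not with appointments.

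Three further weaknesses do not depend on dropout:

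- The test treats six ordered values as unordered categories (5 degrees of freedom), which costs power.
- It yields no interval and no time dimension, although the stated goal is an association over time.
- With five planned interviews, a count of 5 appears to need the baseline interview, whose look-back lies before randomisation.

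What is at stake is the mediation conclusion for appointments: a wrong answer in either direction changes whether that pathway is considered open.

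**Working it through.** **The plan's own figure.** None is given for this test. The only main power figure is for asthma control: 0.82 to 0.87 with 300 patients and a difference of 1/3 SD. A simple two-group calculation (two-sided 5% assumed) has noncentrality (1/3) × √(150/2) = 2.89 and power Φ(2.89 − 1.96) = 0.82, which matches the lower end. It does not feed into what follows.

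**Inputs from the plan.** 1:1 allocation; 301 patients analysed (Appendix A10), taken as 150 per arm; five planned interviews; a 2 × 6 chi-square.

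**Assumed inputs, because the plan gives none.** Probability of a kept appointment per interview 75% in both arms; within-patient correlation 0.3 (beta-binomial); a dropout has 1 to 4 interviews with equal probability, otherwise 5.

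**How the artefact arises.** Mean interviews held at dropout proportion d is 5(1 − d) + 2.5d = 5 − 2.5d. With identical 75% keeping, the mean count is 0.75 × (5 − 2.5d):

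- d = 5%: 0.75 × 4.875 = 3.66
- d = 15%: 0.75 × 4.625 = 3.47
- d = 25%: 0.75 × 4.375 = 3.28

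**Rejection rate with no true effect** (3000 simulated trials per row, nominal 5%):

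| Dropout by arm | Chi-square on count |
|---|---|
| 5% v 5% | about 4% |
| 5% v 8% | about 5% |
| 5% v 10% | about 6% |
| 10% v 15% | about 6% |
| 5% v 15% | about 10% |
| 5% v 25% | about 33% |

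Comparing each patient's share of their own interviews instead gives 4.5% to 6% throughout. Raising the correlation to 0.6 gives 5% to 7% for the count test at gaps of 5 points or less. Monte Carlo error near 5% is about ±0.8 points (1.96 × √(0.05 × 0.95/3000)).

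**A different missingness model.** Suppose a fixed fraction is retained at each of four follow-ups, with keeping of 60% to 90% and correlation 0.3 or 0.5 (1000 trials per setting). Retention of 95% v 92.5% per interview (0.95⁴ = 82% v 0.925⁴ = 73% reaching the fifth) gives 7% to 12%. Retention of 95% v 90% (82% v 66%) gives 13% to 40%. The share-based comparison stays near 5%.

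**Power and masking** (true keeping 80% with home visits v 70% without; dropout model as in the table):

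- Equal 5% dropout: mean counts 0.80 × 4.875 = 3.90 v 0.70 × 4.875 = 3.41. Power is about 61% for the count test and about 85% for the share comparison.
- Home-visit dropout 15% v 5%: mean counts 0.80 × 4.625 = 3.70 v 3.41. The gap shrinks from 0.49 to 0.29. Power is about 27% v 83%.

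**Baseline.** Weeks 0, 12, 24, 36 and 48 make five interviews, so a count of 5 includes week 0 unless interviews after month 12 are counted. The Mediation section uses a look-back of six months, so the week-0 value cannot reflect assignment. Appendix A4 obtained records for the period of participation, which leaves it unclear how the week-0 value was filled. Either way it dilutes the contrast in both arms and does not create a false positive.

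**The case against.** The strongest reply is that the false-positive problem is conditional. It needs completion to differ by arm, which the available text does not show, and dropout is described as limited. At gaps of 5 points or less the test stays close to nominal in the main model, and 25% dropout in one arm would be hard to call limited. This stands, and it rules out a tempting stronger reading: a reader might infer that the arm comparison is in fact biased, or that its true error rate is around 33%. The documents support neither. Nor is an unordered chi-square invalid in itself, since with equal completion it holds its size.

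The reply also notes that this is one of three candidate mediators, that the step from appointments to control is labelled exploratory, with its confounding limits listed, and that Appendix A4 does not make its second analysis depend on the first. A false positive could not establish mediation alone. That also stands and limits the severity. It does not remove the point, because the Mediation section uses the arm-to-mediator association as a screen, and masking would close the pathway wrongly.

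Appendix A4's preference for a binary measure over a count is no answer: it concerns the exposure in the asthma-control model, not this test.

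Finally, any model of interview-level data still conditions on an interview having been held. The section on data collection says staff used the record to find patients at their appointments, so being interviewed may depend on attending. This objection to a GEE alone is sound and is met in the fix.

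**Conclusion.** The point holds in conditional form. The plan's only as-randomised test of appointment keeping uses a count without a denominator, in a study that retains patients with fewer than five interviews and corrects for varying follow-up elsewhere. If completion differs by arm, the test could produce a false effect or hide a real one; whether that happened cannot be told from the text. The rates above rest on assumed keeping, correlation and dropout, and show negligible to modest inflation for small gaps and serious inflation only for large ones. The loss of power, about 61% against 85% under the stated assumptions, needs no difference in dropout. A reader might extend this to the primary result, but the as-randomised contrast in asthma control does not use this count. The change is worth making because it is cheap and the result screens for mediation.

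**What to change.** In Appendix A4, Statistical Methods, replace the chi-square with a logistic GEE on the existing per-interview indicator. Use post-baseline interviews, with terms for arm, clinic, spline time and arm-by-time. Report the arm difference in probability of a kept appointment at 12 months, with the percentile interval from 999 patient-level bootstrap resamples used elsewhere. Interviews after month 12 then enter at their actual times, and the 12-month look-back lies wholly after randomisation. Report the number of interviews completed by arm.

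As a check on interviews held at appointments, define kept appointments from the health-system records in fixed windows from randomisation (for example months 0 to 6 and 6 to 12) for all randomised patients, interviewed or not, so far as the records extend.

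The cost is one model of a kind Appendix A7 already allows for binary outcomes, plus one check; the GEE needs no new data. The GEE assumes interviews are missing completely at random, as the plan's other marginal models do, and this should be stated beside the result.

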Appendix A4 (continued). Appointments kept among asthma patients.

Our estimates of interest were the expected values of asthma control at 0 months and 12 months. Because of the irregular visit times, few patients had visits at exactly 12 months. For that reason, we used predictions from the longitudinal model as of 12 months and then compared them with predictions as of 0 months (date of randomization).

To answer the question of the effect of kept appointments we compared the two scenarios: kept appointments within 6 months of each interview versus did not have any appointments kept within 6 months of the interview. This analysis reflects the more common paradigm for comparing "always exposed" versus "never exposed", where scheduling appointments serves as the exposure. We accomplished this contrast by augmenting the original dataset with two pseudo-datasets, one with all binary values for appointments kept set to 0 and the second with all binary values of appointments kept set to 1. This approach, using data augmentation, is a form of marginal standardization (or predictive margins) as outlined by Korn and Graubard (1999) and as further described by Vittinghoff (2012).

This simplistic approach does not account for several possible sources of confounding. First, we do not factor in time-varying confounders – we adjust only for baseline covariates. Second, we assume that the direction of causation is always from appointment kept to asthma control. The direction of causation could reverse; poorer control could lead to increased need for appointments. We attempted to address that potential problem in two ways. (a) We use the appointment kept from a prior (lookback) period in evaluating it as an exposure for the subsequently reported level of asthma control. (b) We use only a binary indicator for having kept one appointment in a 6 month period rather than a count or continuous measure of appointments kept. A count or continuous measure might be more likely to reflect the degree of prior illness of the patient as the reason for an appointment, while the binary measure more should reflect the anticipated behavior of all asthma patients, who should be seen at least every 6 months. In this fashion we attempted to distinguish patients by their adequate versus inadequate level of ongoing care, and then to determine the association of that measure with asthma control.

Appendix A5. Association of treatment assignment (home visitor versus portal only) and adherence to recommended regimens for inhaler adherence.

Background

One predefined longitudinal measure of the effectiveness of the home visitor versus portal only intervention was inhaler adherence as estimated by the IAS scale (Dolce 1991, Table

1). This validated scale rates adherence based on the following six items.

1. During the last 3 months, have you at times been careless about using your [insert name of inhaled steroid, e.g. Advair, Flovent, Pulmicort, Beclovent, Vanceril, Aerobid Azmacort, QVar]?
2. During the last 3 months, have you ever forgotten to use your [insert name of inhaled steroid]?
3. During the last 3 months, have you ever stopped using your [insert name of inhaled steroid] because you felt better?
4. During the last 3 months, have you ever used your [insert name of inhaled steroid] less than the doctor prescribed because you felt better?
5. During the last 3 months, have you ever stopped using your [insert name of inhaled steroid] because you felt worse?
6. During the last 3 months, have you ever used your [insert name of inhaled steroid] more than the doctor prescribed because you felt you were having breathing problems?

A no response to an item receives a score of 1, and a yes a score of 0, the items are summed, and the total score ranges from 0 (worst) to 6 (best) adherence.

The pre-specified hypothesis was that the intervention might operate on asthma control through improved adherence to inhaler use, i.e. that inhaler use was a potential mediator of the effect of the intervention.

Statistical methods

Using this 7-point scale as the outcome in a longitudinal model that we used for both asthma control and quality of life (time measured by splines and baseline covariates added to the model), we estimated the differences between intervention groups (home visitor versus

Appendix A5 (continued). Association of treatment assignment (home visitor versus portal only) and adherence to recommended regimens for inhaler adherence.

portal use only) in the change in expected values (means of adherence scores) from 0 months to 12 months. As with the other analyses, we estimated confidence bound using the percentile method of 999 bootstrap replications of resampling the data at the patient level and with replacement. We used a marginal model, as implemented by generalized estimating equations with a log link, a gamma family, and a independence working correlation matrix.

Reference

Appendix A6. Effect modification and identification of subgroups.

Over several team meetings, candidate effect modifiers were discussed and a list was generated based on prior knowledge and clinical expertise. The candidate measures include self-reported: Spanish as primary language; specialty or primary care practice site; age group (18-39 years, 40-49 years, > 50 years); education attainment; comorbidities (diabetes, hypertension, high cholesterol, and cancer); hospitalizations; ED visits; intubation; years taking ICS; prednisone usage; food or clothing inadequacy; crowding at home; exposure to violence; lack of housing; lack of utilities; housing instability; smoking status; exposure to second hand smoke; numeracy measured with the ANQ (Apter et al., 2006) reading comprehension measured with S-TOFHLA (Baker et al., 1999) inhaler technique measured using a 7-point scale for a metered dose inhaler and a 6-point scale for a dry powder inhaler, testing the patient on the inhaler used for their inhaled steroid; social support assessed with the Medical Outcome Study Social Support Survey (Sherbourne et al., 1991) privacy concerns with the patient portal assessed using the Portal Use Baseline Survey; depression as measured by the Center for Epidemiologic Studies Depression Scale, a validated 20-item scale (Radloff, 1977) and obesity measured by body mass index. Electronic health literacy was measured with the eHEALS, the eHealth Literacy Scale, an 8-item measure of knowledge, comfort, and perceived skills at finding and evaluating electronic health information (Norman et al., 2006). It has been used in low-income patients (Knapp, 2011). Each item is measured with a 5-point likert scale and the

eHEALS score is the mean of each item. The Scale was administered at the baseline and final data collection. Computer literacy was measured using one question from this scale (“I feel confident in using information from the internet to make health decisions”).

Since one-by-one testing or estimation of candidate effect modifiers has been heavily criticized, the team decided upon groupings of candidate effect variables according to themes (see main report, Table 3). For each theme or group of candidate measures, we implemented a latent class analysis with the goal of reducing the data and the number of candidates.

Estimating latent classes

Latent class analysis was implemented for each group of candidate measures which will distinguish profiles of common responses to the set of variables (McCutcheon, 1987). Latent class regression or finite mixture modeling is concerned with deriving information about a categorical latent variable from observed multivariate response patterns. The method takes advantage of the full data likelihood; therefore, subjects with missing elements contribute to the classification model unless all elements are missing. Full information maximum likelihood, the underlying algorithm, functions with missing data with comparable effectiveness as multiple imputation. The amount of missing data in baseline covariates was small.

Data analysis was performed using Mplus version 7.4, which uses an efficient estimation-maximization algorithm for maximum likelihood estimation (Dempster et al., 1997). The number of latent classes was determined through examination of fit indices and in relation to clinical interpretation of results. Specifically, the Lo-Mendell-Rubin Adjusted Likelihood Ratio Test of model fit (Lo, Mendell, Rubin, 2001) offered a formal comparison of a model with its reduced form. Model estimation yields predicted probabilities of class membership for each individual, which was used to assign an individual to a class or group associated with the highest predicted probability of class membership. The indicator representing the class membership became the moderator variable. Then, the degree of effect modification of the association of the intervention (home visitors) and the key outcome (asthma control) was estimated for each candidate modifier group by testing interactions between the group indicator and the randomization indicator, and time. These preliminary analyses were based on Wald tests for 3-way interactions of time (fit with marginal splines), intervention (home visitor

